12.3.5.3 Tertiary estimand: 'treatment policy'

The tertiary estimand for the primary endpoints will be:

• Treatment difference in response rate after 16 weeks between tralokinumab+TCS and placebo+TCS regardless of rescue medication and treatment discontinuation.

The tertiary estimand assesses the average difference in response rates, resulting from initiation of a treatment regimen with tralokinumab+TCS and additional rescue medication as compared to a treatment regimen with placebo+TCS and additional rescue medication.

Primary analysis for the tertiary estimand

Data retrieved at Week 16 for subjects who have permanently discontinued treatment prior to Week 16 will be included in the analysis.

Imputation of missing data at Week 16 will be done using multiple imputations within 4 groups defined according to randomised treatment arm and whether or not subjects have permanently discontinued IMP prior to Week 16. Within a given treatment arm, retrieved data from discontinued subjects will be used to impute missing data for other discontinued subjects. Similarly, the available data from not discontinued subjects will be used to impute data for such patients where the Week 16 value is missing.

For not discontinued subjects, the stepwise multiple imputations procedure will be conducted in the same way as specified for the primary analysis of the secondary estimand.

For discontinued subjects, it is expected that the number of subjects with retrieved data at Week 16 will be too small to facilitate the same imputation model as mentioned above.

Trial ID: LP0162-1339	Date: 29-Aug-2018	Version: 4.0
		Page 92 of 129

Consequently, an imputation model with only region and baseline effects (IGA as a factor and EASI as a covariate [only for EASI75]) will be applied for discontinued subjects. Some factors may have to be omitted, depending on the observed data, e.g. if retrieved subjects only come from one region or if they all have the same baseline severity.

The imputed datasets will be analysed in the same way as specified for the primary analysis of the secondary estimand.

Sensitivity analyses for the tertiary estimand

Rather than imputing Week 16 data as described in the primary analysis of the tertiary estimand, missing observations will be imputed as 'non-responders'. The assumption reflects that discontinued subjects without retrieved data at Week 16 are more likely to be non-responders than resembling discontinued subjects with retrieved data at Week 16.

12.3.6 Analysis of secondary endpoints

The 3 secondary endpoints evaluate the impact of 16 weeks of treatment on (i) severity and extent of AD, (ii) itch, and (iii) HRQoL. The corresponding endpoints are (i) the change from baseline to Week 16 in SCORAD, (ii) reduction (Y/N) of Worst Daily Pruritus NRS average score for the past week (hereinafter 'Worst Daily Pruritus NRS weekly average') of at least 4 from baseline to Week 16, and (iii) change from baseline to Week 16 in DLQI score. Subject-reported worst daily itch over the last week prior to baseline (Day -6 to 0) will be used to calculate the baseline itch (see also inclusion criterion no. 9).

Reduction of Worst Daily Pruritus NRS weekly average of at least 4 is a binary endpoint, and it will be analysed as described for the primary endpoint EASI75 using all three estimands with the modification of the ANCOVA imputation model that Reduction of Worst Daily Pruritus NRS weekly average replaces EASI where preceding values are used as covariates.

The change from baseline to Week 16 in SCORAD and DLQI, respectively, are continuous endpoints and will be analysed as described below.

All analyses will be based on the full analysis set unless otherwise specified.

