8.2 Inclusion criteria

- 1. Written informed consent and any locally required authorisation obtained from the subject prior to performing any protocol-related procedures, including screening evaluations.
- 2. Age 18 and above.
- 3. Diagnosis of AD as defined by the Hanifin and Rajka (1980) criteria for AD (21; Appendix 4).
- 4. History of AD for ≥ 1 year.
- 5. Subjects who have a recent history (within 1 year before the screening visit) of inadequate response to treatment with topical medications.
 - Inadequate response is defined as failure to achieve and maintain remission or a low disease activity state (comparable to IGA 0=clear to 2=mild) despite treatment with a daily regimen of TCS of medium to higher potency (±TCI as appropriate), applied for at least 28 days or for the maximum duration recommended by the product prescribing information (e.g., 14 days for super-potent TCS), whichever is shorter.
 - Subjects with documented systemic treatment for AD in the past year are also considered as inadequate responders to topical treatments and are potentially eligible for treatment with tralokinumab after appropriate washout.
- 6. AD involvement of ≥10% body surface area at screening and baseline (visit 3) according to component A of SCORAD.
- 7. An EASI score of \geq 12 at screening and 16 at baseline.
- 8. An IGA score of ≥ 3 at screening and at baseline.

Trial ID: LP0162-1339	Date: 29-Aug-2018	Version: 4.0
		Page 40 of 129

- 9. A Worst Daily Pruritus numeric rating scale (NRS) average score of ≥4 during the week prior to baseline.
 - Worst Daily Pruritus NRS at baseline will be calculated from daily assessments of worst itch severity (Worst Daily Pruritus NRS) during the 7 days immediately preceding randomisation (Day -6 to 0). A minimum of 4 Worst Daily Pruritus NRS scores out of the 7 days is required to calculate the baseline average score. For subjects who do not have at least 4 scores reported during the 7 days immediately preceding the planned randomisation date, randomisation should be postponed until this requirement is met, but without exceeding the 6 weeks' maximum duration for screening.
- 10. Subjects must have applied a stable dose of emollient twice daily (or more, as needed) for at least 14 days before randomisation.
- 11. Women of child-bearing potential must use a highly effective* form of birth control (confirmed by the investigator) throughout the trial and at least for 16 weeks (5 half-lives) after last administration of IMP.

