Imputation of missing binary EASI75 data at Week 16 will be done using multiple imputations of the underlying 72-point EASI values within the two groups defined according to randomised treatment arm assuming that data is missing at random within each arm.

- 1. Intermittent missing values will be imputed in each group using a Markov Chain Monte Carlo method to obtain a monotone missing data pattern and 100 copies of the dataset will be generated (seed=290997).
- 2. An ANCOVA model is fitted to the EASI value at Week 2. The model will include effects of baseline EASI as a covariate, and region, and baseline disease severity (IGA 3 or 4) as factors. The estimated parameters, and their variances, will be used to impute missing EASI values at Week 2. 100 copies of the dataset will be generated (seed=111099).
- 3. For each of the 100 copies of the dataset, missing EASI values at Week 4 will be imputed in the same way as for Week 2. The imputations will be based on the same ANCOVA model with effects of baseline EASI as a covariate, and region, and baseline disease severity (IGA 3 or 4) as factors together with the EASI value at Week 2 as covariate. The estimated parameters, and their variances, will be used to impute missing values at Week 4.
- 4. This stepwise procedure will then be repeated sequentially for Week 6, 8, 10, 12, 14, and 16 with the modification that only the EASI values from the preceding two visits will be included as covariates in addition to baseline EASI as a covariate, and region and baseline disease severity as factors. The missing binary EASI75 response at Week 16 will be derived from the corresponding underlying imputed EASI value.

Analysis of Week 16 response

For each of the 100 complete data sets, the difference in response rates (either the IGA 0/1 or the EASI75) between treatment groups will be analysed using the Cochran-Mantel-Haenszel test stratified by region (Europe and North America) and baseline disease severity (IGA 3 or 4). The estimates and standard errors from the 100 analyses will be pooled to one estimated treatment difference and associated standard error using Rubin's rule to draw inference. From these pooled estimates, the 95% CI for the treatment difference will be calculated.

Sensitivity analysis for the secondary estimand

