1. Intermittent missing values will be imputed in each group using a Markov Chain Monte Carlo method to obtain a monotone missing data pattern and 100 copies of the dataset will be generated (seed=290997).

Trial ID: LP0162-1339	Date: 29-Aug-2018	Version: 4.0
		Page 94 of 129

- 2. For each of the 100 copies of the dataset, an ANCOVA model will be fitted to the SCORAD value at Week 2 in the placebo+TCS group. The model will include effects of baseline SCORAD as a covariate, and region and baseline disease severity (IGA 3 or 4) as factors. The estimated parameters, and their variances, will be used to impute missing values at Week 2 for the placebo+TCS group as well as the tralokinumab+TCS group (seed=111099).
- 3. For each of the 100 copies of the dataset, missing values at Week 4 will be imputed in the same way as for Week 2. The imputations will be based on a similar ANCOVA model, but with SCORAD value at Week 2 included as an additional covariate. The parameters from the model will be estimated based on data from the placebo+TCS group. The estimated parameters, and their variances, will be used to impute missing values at Week 4 for both treatment groups.
- 4. This stepwise procedure will then be repeated sequentially for Week 6, 8, 10, 12, 14, and 16 with the SCORAD values from the preceding two visits included as covariates in addition to baseline SCORAD as a covariate, and region and baseline disease severity as factors.

For each of the 100 imputed dataset, the change from baseline in SCORAD at Week 16 will be analysed using an ANCOVA model with effects of treatment, region, baseline disease severity (IGA 3 or 4), and baseline SCORAD value. The estimated difference at Week 16 will be derived together with the associated standard error. The estimates and standard errors from the 100 analyses are pooled to one estimate and associated standard error using Rubin's rule to draw inference. From these pooled estimates, the 95% CI for the treatment difference will be calculated.

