12.3.6.2 Secondary estimand for the continuous secondary endpoints: 'treatment policy'

The secondary estimand for the continuous secondary endpoints will be:

• Treatment difference in change from baseline to Week 16 in SCORAD and DLQI, respectively, between tralokinumab+TCS and placebo+TCS regardless of rescue medication use and treatment discontinuation.

The secondary estimand assesses the average difference in change from baseline in SCORAD and DLQI after 16 weeks, resulting from initiation of a treatment regimen with tralokinumab+TCS and additional rescue medication as compared to a treatment regimen with placebo+TCS and additional rescue medication.

Trial ID: LP0162-1339	Date: 29-Aug-2018	Version: 4.0
		Page 95 of 129

Primary analyses for the secondary estimand (continuous secondary endpoints)

Data retrieved at Week 16 for subjects who have permanently discontinued IMP prior to Week 16 will be included in the analysis. Missing Week 16 data will be imputed using multiple imputations assuming that data is missing at random within the groups used for imputation.

Imputation of missing data at Week 16 will be done using multiple imputations within 4 groups defined according to randomised treatment arm and whether or not subjects have discontinued treatment prior to Week 16. Within a given treatment arm, retrieved data from discontinued subjects will be used to impute missing data for other discontinued subjects. Similarly, the available data from not discontinued subjects will be used to impute data for such subjects where the Week 16 value is missing.

For not discontinued subjects, the stepwise multiple imputations procedure will be conducted in the same way as specified for the imputation of the underlying EASI values in the primary analysis of the secondary estimand for the binary endpoints.

For discontinued subjects, it is expected that the number of subjects with retrieved data at Week 16 will be too small to facilitate the same imputation model as mentioned just above. Consequently, an imputation model with only region and baseline effects (IGA as a factor and baseline SCORAD / DLQI as a covariate) will be applied for discontinued subjects. Some factors may have to be omitted, depending on the observed data, e.g. if retrieved subjects only come from one region or if they all have the same baseline severity.

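### The imputation model for the pruritus responder endpoint keeps baseline EASI and leaves out baseline pruritus NRS; only the supportive estimands are affected, and only slightly

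*Protocol*

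**What the plan says.** Section 12.3.6 applies all three estimands to the pruritus responder endpoint and borrows the EASI75 method with one stated modification: "Reduction of Worst Daily Pruritus NRS weekly average replaces EASI where preceding values are used as covariates".

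The borrowed model is in section 12.3.5.2. Its first step, for Week 2, reads: "The model will include effects of baseline EASI as a covariate, and region, and baseline disease severity (IGA 3 or 4) as factors". Week 4 adds the Week 2 value. From Week 6 onward "only the EASI values from the preceding two visits will be included as covariates in addition to baseline EASI as a covariate", again with region and baseline severity as factors. The copy-reference sensitivity analysis uses the same steps.

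For subjects who stopped IMP before Week 16, the treatment-policy analysis in section 12.3.5.3 uses "an imputation model with only region and baseline effects (IGA as a factor and EASI as a covariate [only for EASI75".

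The continuous secondary endpoints are handled differently. The SCORAD imputation in section 12.3.6.1, applied also to DLQI, takes the preceding values "in addition to baseline SCORAD as a covariate". The reduced model for discontinued subjects in section 12.3.6.2 has "IGA as a factor and baseline SCORAD / DLQI as a covariate".

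Entry criterion 9 in section 8.2 requires "A Worst Daily Pruritus numeric rating scale (NRS) average score of ≥4 during the week prior to baseline", on a scale from 0 to 10.

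**The concern.** A responder is defined by the fall from the subject's own baseline itch, so baseline itch strongly predicts who can be expected to respond. The written model conditions on baseline EASI, a measure of skin signs and extent, and not on baseline itch. If subjects with high (or low) baseline itch are more often missing, their imputed response is drawn from a model that does not allow for where they started.

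The gap is widest where no post-baseline itch value is available to stand in for the baseline: at the Week 2 step, and in the reduced model for discontinued subjects. At stake are the hypothetical and treatment-policy estimates for an endpoint in the secondary family.

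**Working it through.** **1. Which terms the modification reaches**

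| Imputation model | Own baseline of the endpoint in the model? |
|---|---|
| EASI75, section 12.3.5.2 | Yes, baseline EASI |
| SCORAD and DLQI, section 12.3.6.1 (copy-reference) | Yes |
| SCORAD and DLQI, section 12.3.6.2 (discontinued subjects) | Yes |
| Pruritus, stepwise model (12.3.6 applied to 12.3.5.2) | No; baseline EASI remains |
| Pruritus, discontinued subjects (12.3.6 applied to 12.3.5.3) | No |

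Section 12.3.5.2 lists the preceding visits in addition to baseline EASI, so they are two different terms and only the first is replaced. Counting baseline as a preceding value does not help. The substituted quantity is the reduction, which at baseline is b − b = 0 for everyone. In the reduced model there are no preceding values to replace. EASI is bracketed there as applying to EASI75 only, so pruritus either inherits baseline EASI or has no such covariate. Neither reading brings in baseline itch.

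**2. Why the starting value matters**

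Response requires b − y ≥ 4, a proportional fall of 4/b. For b = 4 this is 100% (y must be 0). For b = 7.5 it is 4/7.5 = 53%. For b = 10 it is 40% (y at most 6).

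**3. Which analyses use the model**

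Section 12.3.4 puts only the primary analysis of the primary estimand into the test hierarchy. For this endpoint that is the composite estimand of section 12.3.5.1, where missing subjects count as non-responders. The regression imputation feeds only the hypothetical and treatment-policy estimands. No figure in the protocol depends on it. The stated 90% power for IGA 0/1 reproduces without it: pooled rate (123 × 0.15 + 246 × 0.30)/369 = 0.25, null SE 0.0478, alternative SE 0.0435, (0.15 − 1.96 × 0.0478)/0.0435 = 1.29, power 90.2%.

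**4. Size, on assumed data**

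The protocol gives no baseline NRS distribution or missing rate, so everything in this step is assumption.

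*Stepwise model, error in each arm.* Baseline NRS was normal with mean 7.5 and SD 1.5, truncated to 4–10. Drop-out was more likely with higher baseline and higher last NRS. True response was about 43% (n = 246) and 22% (n = 123); 200 replicates. Baseline EASI was kept in all four models. Errors are in percentage points, active / placebo:

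| Imputed variable and baseline terms | 8.0% / 9.9% missing | 18.2% / 21.5% missing |
|---|---|---|
| Reduction, no baseline NRS | −0.17 / −0.13 | −0.76 / −0.57 |
| Reduction, with baseline NRS | +0.37 / +0.21 | +0.56 / +0.24 |
| NRS value, no baseline NRS | +0.48 / +0.45 | +0.87 / +0.98 |
| NRS value, with baseline NRS | +0.30 / +0.19 | +0.46 / +0.12 |

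Active minus placebo, the error in the treatment difference is −0.04 and −0.19, +0.16 and +0.32, +0.03 and −0.11, +0.11 and +0.34 in row order. All are below 0.4 points. When the reduction is modelled, missing subjects with baseline below 6 are imputed as responders too often by 9–21 points without baseline NRS and by 4–12 points with it.

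*Treatment difference directly.* Baseline mean 7.7 (SD 1.5), 10% and 12% missing, true response about 37% and 15%, so a difference of about 22 points:

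| Missingness and baseline itch | No preceding values | Two preceding visits |
|---|---|---|
| Unrelated | about 0 | about 0 |
| Related, same direction in both arms | about 0.5 | 0.2–0.3 |
| Related, opposite directions | 1.3 | 0.8 |

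The largest entry is 1.3/22, about 6% of the assumed difference.

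**The case against.** Several points on the other side stand.

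- A reader might infer that the confirmatory pruritus result is biased. It is not: the test under Holm uses non-responder imputation and never calls this model, so type I error control is untouched.
- A reader might infer that baseline NRS decides whether a 4-point fall is possible at all. Criterion 9 sets the minimum at 4, so every eligible subject can reach it. Baseline sets how hard it is.
- A reader might infer that discontinued subjects are imputed with no itch information. Section 12.3.5.3 imputes them from the retrieved itch outcomes of discontinued subjects in the same arm. What is lacking is the individual subject's baseline itch.
- The situation without preceding values should be limited. Under the hypothetical estimand it covers subjects with no usable itch value at Week 2. Under treatment policy it covers discontinued subjects whose Week 16 value is also missing, although section 8.5 and Panel 3 ask them to attend the nominal Week 16 visit and keep the diary until then.
- Other analyses give partial cover. The treatment-policy estimand has a non-responder sensitivity analysis. Section 12.3.7 analyses the change in pruritus NRS with the repeated measurements model, which includes the endpoint's own baseline.
- The numerical gain from the fix is modest. In the stepwise simulation, adding baseline NRS reduced the arm-level error when the NRS value was imputed. It did not clearly do so when the reduction was imputed, and it did not reduce the already small error in the treatment difference.

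It may also be a drafting slip that the statistical analysis plan corrects. That does not remove the point: the protocol does not leave the model open but fixes its covariates, steps and seeds.

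**Conclusion.** The point holds as a minor specification fault in supportive analyses. As written, pruritus is the only secondary endpoint whose imputation model lacks its own baseline, and no reading of sections 12.3.5.2, 12.3.5.3 and 12.3.6 supplies it. That conclusion rests on the text alone.

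The size rests on assumed baseline itch, missing rates and drop-out patterns. The error in the treatment difference is about zero if missingness is unrelated to baseline itch. It is a few tenths of a point in the ordinary related case, and reaches 1.3 points only when the relation runs in opposite directions in the two arms and no preceding values exist. A claim of material bias, or of any effect on the confirmatory conclusion, is not supported. The case for the change is consistency with the protocol's own practice and a better-chosen covariate.

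**What to change.** Replace the modification in section 12.3.6 with a sentence to this effect: for the pruritus endpoint, the Worst Daily Pruritus NRS weekly average takes the place of EASI throughout the imputation model, as the imputed variable, as the baseline covariate and as the preceding-visit covariates; in the model for discontinued subjects, baseline NRS is the covariate beside region and baseline IGA; the reduction of at least 4 is then derived from observed baseline minus the imputed Week 16 value. This also settles whether the NRS value or its reduction is imputed, which the present wording leaves unclear. The copy-reference sensitivity analysis inherits the change.

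The cost is one sentence. The baseline average is already required before randomisation by criterion 9, and neither the sample size nor the test hierarchy changes. The statistical analysis plan update that section 12.3.12 foresees before unblinding is a suitable place if no further amendment is planned.

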12.3.6.1 Primary estimand for the continuous secondary endpoints: 'hypothetical'

The primary estimand for the continuous secondary endpoints will be:

Trial ID: LP0162-1339	Date: 29-Aug-2018	Version: 4.0
		Page 93 of 129

 Treatment difference in change from baseline to Week 16 in SCORAD and DLQI, respectively, if all subjects adhered to the treatment regimen in the sense that they did not discontinue IMP permanently and no rescue medication was made available before Week 16.

The primary estimand assesses the expected benefit when adhering to the treatment regimen tralokinumab+TCS with no rescue medication as compared to a treatment regimen with placebo+TCS with no rescue medication.

Primary analysis of the primary estimand (continuous secondary endpoints)

Data collected after permanent discontinuation of IMP or after initiation of rescue medication will not be included in the analysis.

The endpoints will be analysed using a repeated measurements model on the post baseline responses up to Week 16 with an unstructured covariance matrix, Kenward-Roger approximation to estimate denominator degrees of freedom, and the mean modelled as follows (shown for change from baseline in SCORAD):

Change from baseline in SCORAD

= treatment × visit + baseline SCORAD × visit + region + baseline IGA

This model assumes that data is missing at random within each treatment arm. The estimates will be presented with nominal p-values and 95% CI at each visit. The primary comparison between tralokinumab+TCS and placebo+TCS will be at Week 16.

Sensitivity analysis for the primary estimand (continuous secondary endpoints)

Rather than assuming that observations are missing at random within each treatment arm it is assumed that missing data from subjects who discontinue treatment/receive rescue medication in the tralokinumab+TCS arm will resemble data from subjects from the placebo+TCS arm who do not discontinue treatment/receive rescue medication. Imputation of missing data at Week 16 will be done using a pattern mixture model where missing data in the tralokinumab+TCS arm as well as the placebo+TCS arm will be imputed from the placebo+TCS arm (using a so-called copy-reference approach). The procedure for the change from baseline in SCORAD at Week 16 is described below. The same procedure will be applied for the DLQI endpoint.

1. Intermittent missing values will be imputed in each group using a Markov Chain Monte Carlo method to obtain a monotone missing data pattern and 100 copies of the dataset will be generated (seed=290997).

Trial ID: LP0162-1339	Date: 29-Aug-2018	Version: 4.0
		Page 94 of 129

- 2. For each of the 100 copies of the dataset, an ANCOVA model will be fitted to the SCORAD value at Week 2 in the placebo+TCS group. The model will include effects of baseline SCORAD as a covariate, and region and baseline disease severity (IGA 3 or 4) as factors. The estimated parameters, and their variances, will be used to impute missing values at Week 2 for the placebo+TCS group as well as the tralokinumab+TCS group (seed=111099).
- 3. For each of the 100 copies of the dataset, missing values at Week 4 will be imputed in the same way as for Week 2. The imputations will be based on a similar ANCOVA model, but with SCORAD value at Week 2 included as an additional covariate. The parameters from the model will be estimated based on data from the placebo+TCS group. The estimated parameters, and their variances, will be used to impute missing values at Week 4 for both treatment groups.
- 4. This stepwise procedure will then be repeated sequentially for Week 6, 8, 10, 12, 14, and 16 with the SCORAD values from the preceding two visits included as covariates in addition to baseline SCORAD as a covariate, and region and baseline disease severity as factors.

For each of the 100 imputed dataset, the change from baseline in SCORAD at Week 16 will be analysed using an ANCOVA model with effects of treatment, region, baseline disease severity (IGA 3 or 4), and baseline SCORAD value. The estimated difference at Week 16 will be derived together with the associated standard error. The estimates and standard errors from the 100 analyses are pooled to one estimate and associated standard error using Rubin's rule to draw inference. From these pooled estimates, the 95% CI for the treatment difference will be calculated.

